and/or unphosphorylated levels of IGF pathway biomarkers that may include but are not limited to IGF receptor type 1 (IGF-1R), insulin receptor substrate-1 (IRS-1), mitogen-activated protein kinase (MAPK), insulin receptor (IR), antigen identified by monoclonal antibody Ki-67 (Ki67), caspase 3, and/or protein kinase B signaling protein (pAkt). Deoxyuride-5'-triphosphate biotin nick end labeling (TUNEL) analysis may also be performed. Evaluation of levels of proteins in the voided urine that may include but are not limited to IGF-1, IGF-2, IGFBPs, nuclear matrix protein (NMP) will be evaluated and their relationship with clinical outcome explored. For the dose-expansion phase, the expression level of IGF pathway-related factors such as IGF-1R on subject response to treatment will be evaluated in circulating tumor cells and tumor cells in urine.

MEDI-573 will be administered once every week as [REDACTED] IV infusion [REDACTED] [REDACTED] or as a [REDACTED] IV infusion for doses [REDACTED]. As a monoclonal antibody, IV administration is the only convenient and safe route that will ensure adequate bioavailability. The length of infusion in the clinical protocol is increased compared to the GLP toxicology study in order to minimize the possibility of infusion-related adverse events (AEs).

MEDI-573 is supplied as a sterile lyophilized product in single-use 10 mL vials. The product is reconstituted with sterile water [REDACTED] prior to clinical use.

2 Study Objectives and Overview

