2.3 Exploratory Objectives

The exploratory objectives of this study are to:

- 1) Determine levels of circulating soluble proteins that may include but are not limited to growth hormone (GH), IGF-binding proteins (IGFBPs), insulin, and glucose, and explore associations with clinical outcome;
- 2) Assess levels of phosphorylated and/or unphosphorylated factors in specimens. These factors may include but are not limited to IGF receptor type 1 (IGF-1R), insulin receptor substrate-1 (IRS-1), mitogen-activated protein kinase (MAPK), insulin receptor (IR), antigen identified by monoclonal antibody Ki-67 (Ki67), caspase 3, and/or protein kinase B signaling protein (Akt) in archived tumor biopsies, biopsies obtained during surgical procedures in the course of routine patient care, and/or exfoliated cells collected in voided urine, catheterized urine and/or bladder washes. Deoxyuride-5'-triphosphate biotin nick end labeling (TUNEL) analysis may also be performed.
- 3) Evaluate the relationship of IGF pathway-related components at the mRNA and miRNA level, including IR-A mRNA level in tumor biopsies obtained pre- and post-MEDI-573 treatment using TaqMan qRT-PCR assays and microarray studies.
- 4) Evaluate the relationship of IGF pathway-related factors including IR expression levels using whole genome array and subject tumor response to MEDI-573.
- 5) Perform genomics and proteomics analyses on exfoliated cells collected in bladder washings from selected subjects in the dose-expansion phase
- 6) For the dose-expansion phase, evaluate the expression level of IGF pathway-related factors such as IGF-1R on subject response to MEDI-573 when circulating tumor cells are available.
- 7) For the dose-expansion phase, evaluate the levels of proteins in urine that may include but are not limited to IGF-1, IGF-2, IGFBPs, and nuclear matrix protein (NMP), and explore their relationship with clinical outcome.

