ⁱ Serum chemistry includes AST/ALT, total bilirubin, creatinine (and creatinine clearance at Screening), alkaline phosphatase, sodium, potassium, chloride, phosphorous, calcium, glucose, albumin, magnesium, LDH; TSH will be measured at Day 1 of each new cycle and at the end of treatment. ^j Routine with microscopy; collected prior to or 48 hours after any cystoscopic procedures. ^k PK samples will be collected at the following timepoints: Cycle 1 Day 1, pre-infusion and immediately post completion of infusion (±5 minutes), 2 hours ±15 minutes and 6 hours ±15 minutes post infusion; Day 2 at 24 hours post Day 1 infusion ±2 hours; Day 3 at 48 hours post Day 1 infusion ±2 hours; Day 8 and Day 15 pre- and post-infusion; Subsequent cycles treatment Days 1, 8, and 15 immediately prior to and post-infusion; and at the time of treatment discontinuation and 21 and 30 days after the last dose of MEDI-573. ^l Sample collection for anti-MEDI-573 antibodies should be done pre dose (prior to MEDI-573 administration). ^m Timepoints for biomarker collections are listed in Section 3.7.6.1. Insulin and GH are collected at one timepoint per visit. Tumor markers are collected as clinically indicated. ⁿ In the dose-escalation and dose-expansion phases, if an archived tumor sample is available and the subject provides consent, the sample is collected at screening only; Collect and ship per instructions in the Specimen Collection Manual. ^o In dose-escalation and dose-expansion phases, includes any biopsy tissue from intermediate timepoints as routine clinical management permits (optional). ^p Sample collection for circulating tumor cells in blood should be done prior to MEDI-573 administration. ^q In the dose-expansion phase only, samples will be collected at two timepoints: prior to the first treatment in Cycle 1, and after the last dose on Cycle 1 but prior to administration of the first dose of Cycle 2 and should be done at the same timepoint for all specimen types. ^r Sample collection for exfoliated urothelial cells (dose-expansion phase only) should be done prior to MEDI-573 administration.												

Table 3.6-2 Schedule of Subject Evaluations: Screening and Treatment Periods (Dose Escalation Cohorts 6 and 7 Only)

Evaluation	Screen ^a	Cycle 1				Cycle 2 and Every Cycle Thereafter		Every 2 Cycles	End of Treatment ^b
		Day 1	Day 2	Day 3	Day 8	Day 1	Day 8		
Written informed consent and HIPAA	X								
Verify eligibility criteria	X	X							
Medical history	X								

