 - Serum chemistry (AST/ALT, total bilirubin, creatinine, alkaline phosphatase, sodium, potassium, chloride, phosphorus, calcium, glucose, albumin, magnesium, and LDH)
 - Serum concentration of MEDI-573

- Blood biomarker analysis
- 2) Urine collection prior to administration of MEDI-573
 - Urinalysis (routine urinalysis with microscopy, Cohorts 1 through 5 and the expansion phase only)
 - Urine for analysis of soluble factors (dose-expansion cohort only)
- 3) Vital signs (temperature, respiration rate, pulse, blood pressure) immediately prior to MEDI-573 infusion; at every 15 minutes (\pm 5 minutes) during the infusion; at the end of the infusion (\pm 5 minutes); and 30 and 60 minutes (\pm 5 minutes) after completion of the infusion.
- 4) Administration of MEDI-573 (Cohorts 1 through 5 and the expansion phase only)
- 5) Blood collection immediately post infusion of MEDI-573 (\pm 5 minutes, Cohorts 1 through 5 and the expansion phase only)
 - Serum concentration of MEDI-573
 - Blood biomarker analysis
- 6) AE/SAE assessment
- 7) Concomitant medications

Cycle 1: Day 15 (Cohorts 1 through 5 and Dose Expansion Phase only)

- 1) Blood collection prior to administration of MEDI-573
 - Hematology (CBC with differentials, platelets)
 - Serum chemistry (AST/ALT, total bilirubin, creatinine, alkaline phosphatase, sodium, potassium, chloride, phosphorus, calcium, glucose, albumin, magnesium, and LDH)
 - Serum concentration of MEDI-573
 - Blood biomarker analysis
- 2) Urine collection prior to administration of MEDI-573
 - Urinalysis (routine urinalysis with microscopy)
 - Urine for analysis of soluble factors (dose-expansion cohort only)
- 3) Vital signs (temperature, respiration rate, pulse, blood pressure) immediately prior to infusion of MEDI-573; at every 15 minutes (\pm 5 minutes) during the infusion; at the end of the infusion (\pm 5 minutes); and 30 and 60 minutes (\pm 5 minutes) after completion of the infusion.
- 4) Administration of MEDI-573
- 5) Blood collection immediately post infusion of MEDI-573 (\pm 5 minutes)
 - Serum concentration of MEDI-573

- Blood biomarker analysis
- 6) AE/SAE assessment
- 7) Concomitant medications

Day between \geq Cycle 1, Day 15 and \leq Cycle 2, Day1 (exclusive; Dose Expansion Phase only)

The following samples will be collected after the last dose on Cycle 1 but prior to administration of the first dose on Cycle 2:

- Whole blood for RNA analysis
- Tumor biopsies

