- Exfoliated urothelial cells and analysis of soluble factors (from urine or bladder washes; dose-expansion cohort only)
- Urothelial cells (from urine, dose-expansion cohort only)

Cycle \geq 2: Day 1 (All Subjects Unless Otherwise Specified)

The following evaluations will be performed on Day 1 of every cycle (ie, every 3 weeks), unless otherwise indicated, starting at Cycle 2:

- 1) Physical examination for evaluation of disease state
- 2) Update concomitant medications
- 3) Obtain body weight for dosing calculations
- 4) Blood collection prior to administration of MEDI-573
 - Hematology (CBC with differentials, platelets)
 - Serum chemistry (AST/ALT, total bilirubin, creatinine, alkaline phosphatase, sodium, potassium, chloride, phosphorus, calcium, glucose, albumin, magnesium, LDH and TSH)
 - Serum concentration of MEDI-573 (blood sample collected immediately prior to MEDI-573 infusion)
 - Blood biomarker analysis
 - Circulating tumor cells
 - Anti-MEDI-573 antibodies
- 5) Urine collection prior to administration of MEDI-573
 - Urine β hCG (women of childbearing potential only)
 - Urinalysis (routine urinalysis with microscopy)

- Exfoliated urothelial cells and analysis of soluble factors (from urine or bladder washes; dose-expansion cohort only)
- 6) Administration of MEDI-573
 - 7) Blood collection immediately post infusion of MEDI-573 (\pm 5 minutes)
 - Serum concentration of MEDI-573
 - Blood biomarker analysis
 - 8) Vital signs (temperature, respiration rate, pulse, blood pressure) immediately prior to infusion of MEDI-573; every 15 minutes (\pm 5 minutes) during the infusion; at the end of the infusion (\pm 5 minutes); and 30 and 60 minutes (\pm 5 minutes) after completion of the infusion.
 - 9) ECG (12-lead) (immediately prior to infusion of MEDI-573 only) All ECGs will be obtained in triplicate, ie, 3 ECGs should be obtained within approximately a 5-minute time interval.
 - 10) AE/SAE assessment
 - 11) Karnofsky performance status

Cycle \geq 2: Day 8 (All Subjects Unless Otherwise Specified)

The following evaluations will be performed on Day 8 of every cycle, unless otherwise indicated, starting at Cycle 2:

- 1) Update concomitant medications
- 2) Blood collection prior to administration of MEDI-573
 - Hematology (CBC with differentials, platelets)
 - Serum chemistry (AST/ALT, total bilirubin, creatinine, alkaline phosphatase, sodium, potassium, chloride, phosphorus, calcium, glucose, albumin, magnesium, and LDH)

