The levels of IGF-1 and IGF-2 suppression by MEDI-573 determined during dose-escalation will be used to determine the dose administered to subjects enrolled in the dose-expansion phase of the study. In the dose-expansion phase of the study, exfoliated cells from voided urine, catheterized urine, and/or (in the case of subjects with bladders who may be undergoing cystoscopic procedures) bladder washings will be taken at Screening, on Day 1 of Cycle 2 and every cycle thereafter, and the End of Treatment. Cells and proteins from voided urine will be obtained from urine samples collected at Screening, Days 1, 8, and 15 of Cycle 1, on Days 1 and 15 of Cycle 2 and every cycle thereafter, and the End of Treatment. An additional sample for exfoliated urothelial cells from bladder washes or urine will be collected after the last dose on Cycle 1 but prior to administration of the first dose on Cycle 2.

Circulating tumor cells will be taken at Screening, on Days 1 of Cycle 2 and every cycle thereafter, and the End of Treatment and will be analyzed by the Sponsor.

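### Section 3.6 lets urinary proteins be measured in bladder washes at some visits, against Sections 1.6 and 3.7.6.1, and leaves that urine outside the cystoscopy timing rule (exploratory objective 7 only)

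*Protocol*

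**What the plan says.** Exploratory objective 7 (Section 2.3) is, for the expansion phase, to "evaluate the levels of proteins in urine that may include but are not limited to IGF-1, IGF-2, IGFBPs" and nuclear matrix protein, and to explore their relationship with clinical outcome.

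The protocol describes the specimen in two ways.

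- **Urine.** Section 1.6 plans "Evaluation of levels of proteins in the voided urine that may include but are not limited to IGF-1, IGF-2, IGFBPs, nuclear matrix protein (NMP". Section 3.7.6.1 states "Cells and proteins from voided urine will be obtained from urine samples collected at Screening, Days 1, 8, and 15 of Cycle 1", then lists later visits. Table 3.6-1 labels its soluble-factor row as urine. The Section 3.6 lists for Cycle 1 Days 1, 8 and 15 and for Day 15 of later cycles read "Urine for analysis of soluble factors (dose-expansion cohort only".
- **Urine or wash.** The Section 3.6 lists for Screening, the window after the last Cycle 1 dose, Day 1 of Cycle 2 onward, and End of Treatment read "Exfoliated urothelial cells and analysis of soluble factors (from urine or bladder washes; dose-expansion cohort only".

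On timing, footnote j of Table 3.6-1 qualifies urinalysis: "Routine with microscopy; collected prior to or 48 hours after any cystoscopic procedures". The soluble-factor row has no such note. Footnote q, attached to the window entries for tumor biopsy, exfoliated cells and soluble-factor urine, says that collection "should be done at the same timepoint for all specimen types". It gives no order.

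**The concern.** A bladder wash is fluid put into the bladder and recovered. Its protein concentration depends on the instilled and residual volumes, so it cannot be compared directly with urine from the same subject. If sites may choose either specimen at some visits but not at others, a change over time can reflect the choice of specimen.

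Footnote j shows that the plan recognises that cystoscopy disturbs urine, yet the guard stops at urinalysis. Blood carries IGF-1, IGF-2 and their binding proteins, which are the quantities objective 7 measures. After a biopsy of the urinary tract, blood in the sample would add them directly. Mixed or contaminated samples from this small group cannot be collected again later.

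**Working it through.** The protocol gives no figure to reproduce, so the check is mainly a comparison of the text.

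**1. Specimen by visit (Section 3.6 lists, expansion phase)**

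| Visit | Specimen allowed for soluble factors |
|---|---|
| Screening | urine or wash |
| Cycle 1 Day 1, pre-infusion | urine |
| Cycle 1 Day 8, pre-infusion | urine |
| Cycle 1 Day 15, pre-infusion | urine |
| Between last Cycle 1 dose and Cycle 2 | urine or wash |
| Cycle 2 onward, Day 1 | urine or wash |
| Cycle 2 onward, Day 15 | urine |
| End of Treatment | urine or wash |

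A subject can therefore move between the two specimens several times. Section 3.7.6.1 describes the extra window sample as one for exfoliated cells only, whereas Section 3.6 and Table 3.6-1 also take soluble factors then.

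**2. Illustration of dilution.** Assumptions, not in the protocol: 50 to 100 mL instilled over 10 to 50 mL residual urine, with complete mixing. Dilution d = (instilled + residual) / residual.

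- Low: (50 + 50) / 50 = 2
- High: (100 + 10) / 10 = 11

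The apparent change from urine to wash with no true change is 1 − 1/d: 1 − 1/2 = 50%, and 1 − 1/11 = 91%. A switch from wash to urine gives a spurious 2- to 11-fold rise.

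**3. Timing.** The last Cycle 1 dose is on Day 15. Cycle 2 starts 7 days later (Section 3.5.2), on Day 22. The Table 3.6-1 window runs to Day 21. A biopsy on Day 21 is about one day before the Cycle 2 Day 1 urine, inside 48 hours. Footnote j guards the urinalysis specimen at that visit but not the soluble-factor specimen. The window sample itself may be taken with the biopsy. A pre-treatment biopsy on the day before Cycle 1 Day 1 leaves the same gap at baseline.

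**4. Illustration of blood.** Section 1.1 gives mean levels in bladder cancer cases: IGF-1 175.8 ng/mL and IGFBP-3 2,632.9 ng/mL. Assumptions: plasma is 60% of blood, and blood is 0.1% to 1% of sample volume.

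- IGF-1: 175.8 × 0.6 × 0.001 = 0.11 ng/mL; × 0.01 instead = 1.05 ng/mL
- IGFBP-3: 2,632.9 × 0.6 × 0.001 = 1.6 ng/mL; × 0.01 instead = 15.8 ng/mL

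The protocol gives no usual urinary level, so these additions cannot be called large or small. Equal bleeding before and after treatment need not cancel. Section 1.6 reports complete suppression of circulating IGF-1 and IGF-2 at 5, 10 and 15 mg/kg, so if the assay reads free IGF, blood would raise a baseline sample more than a post-dose one.

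**The case against.** The strongest reply is that the intended specimen is already clear. Two sections name voided urine for proteins, the table row says urine, and Section 2.4 mentions washings only as a source of cells. The visit-list line may simply join two specimens under one parenthesis. That is a fair reading of the intent, but the visit lists are what a site follows, and four of them permit a wash. The inconsistency stands.

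A reader might infer that objective 7 cannot be answered, or that baseline and the first post-treatment urine are both exposed to biopsy bleeding. The documents do not support either. The first post-treatment sample is Cycle 1 Day 8, about eight days after a biopsy done on the day before Cycle 1 Day 1. The Day 15 sample is taken before that day's dose, and the second biopsy follows the dose. Both samples are urine only, as are Cycle 1 Day 1 and Day 15 of later cycles, so a single-specimen series exists.

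Four further limits stand:

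- Biopsies may be of metastases, under image guidance, including in subjects without bladders. Washings arise only in some subjects with bladders.
- The same timepoint in footnote q may mean the same window, not the same procedure.
- Footnote q is not attached to the Screening urine.
- Creatinine correction may be in the statistical analysis plan or the Specimen Collection Manual, neither of which is shown. Its absence here is no fault.

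**Conclusion.** The point holds, at low severity. Section 3.6 contradicts Sections 1.6 and 3.7.6.1, the Table 3.6-1 row label and its own other visit lists on the specimen for urinary proteins. It permits a mixture that can bias changes at Screening, the window sample, Day 1 of Cycle 2 onward and End of Treatment.

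Blood contamination is possible, not certain. It concerns subjects whose biopsy is from the urinary tract, at the window sample, the Cycle 2 Day 1 sample and, if the pre-treatment biopsy is close to it, the baseline sample. The number affected is an unknown subset of about 20 subjects. The 50% to 91% apparent fall and the amounts of added protein depend wholly on the assumed volumes and blood fractions.

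Only exploratory objective 7 at those visits is concerned. Safety, the dose-finding objective, circulating IGF-1 and IGF-2, and antitumor activity do not use these samples.

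**What to change.** - In the four visit lists, separate the two items: urine for soluble factors, in line with Sections 1.6 and 3.7.6.1, and bladder washes as an option for exfoliated cells only. If catheterized urine is to be acceptable for proteins, those two sections should say so too.
- Extend footnote j's timing rule to the soluble-factor urine row of Table 3.6-1.
- In footnote q, state that this urine is collected before any cystoscopic biopsy at that timepoint.
- Make Section 3.7.6.1 agree with Section 3.6 on whether the window sample includes soluble factors.

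Creatinine normalization is optional and may already be planned elsewhere. The cost is wording in the protocol and, where needed, the Specimen Collection Manual. No visit or procedure is added.

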3.7 Subject Evaluation Methods

3.7.1 Routine Laboratory Evaluations

Routine laboratory tests (hematology, serum chemistry, and urinalysis) during Screening and during the study will be performed in a licensed local clinical laboratory. Serum or urine pregnancy tests during the study will be performed in the clinic using a licensed test. Abnormal laboratory results should be repeated as soon as possible (preferably within 24 to 48 hours).

Creatinine clearance (CrCl) will be calculated using the Cockcroft-Gault formula ([Cockcroft and Gault, 1976](#)) as follows:

For women:

$$\text{CrCl} = \frac{[140 - \text{Age (years)}] \times \text{Mass (kg)}}{72 \times \text{serum creatinine (mg/dL)}} \times 0.85$$

OR

$$\text{CrCl} = \frac{[140 - \text{Age (years)}] \times \text{Mass (kg)}}{815 \times \text{serum creatinine (mmol/L)}} \times 0.85$$

For men:

$$\text{CrCl} = \frac{[140 - \text{Age (years)}] \times \text{Mass (kg)}}{72 \times \text{serum creatinine (mg/dL)}}$$

OR

$$\text{CrCl} = \frac{[140 - \text{Age (years)}] \times \text{Mass (kg)}}{815 \times \text{serum creatinine (mmol/L)}}$$

3.7.2 Physical Examinations

Physical examinations will be performed as described in [Table 3.6-1](#) and [Table 3.6-2](#) (Schedule of Subject Evaluations: Screening and Treatment Periods) and [Table 3.6-3](#) (Schedule of Subject Evaluations: Follow-up Periods) and will include assessments of the of the head, eyes, ears, nose, and throat (HEENT), respiratory, cardiovascular, GI, urogenital, musculoskeletal, neurological, psychiatric, dermatological, hematologic/lymphatic, and endocrine systems; and height (at Screening only).

Vital signs (temperature, respiration rate, pulse, blood pressure) immediately prior to MEDI-573 infusion, at every 15 minutes during the infusion, at the end of the infusion (± 5 minutes) and 30 and 60 minutes (± 5 minutes) after completion of the infusion.

3.7.3 Electrocardiographic Evaluations

Twelve-lead ECGs will be performed as described in [Table 3.6-1](#) and [Table 3.6-2](#). Electrocardiogram equipment, with instant print out and electronic transmission capabilities, and training will be provided to all study sites. All ECGs performed during the study will be

obtained in triplicate, ie, 3 ECGs should be obtained within a 5 minutes time period. ECGs will be collected at Screening, Cycle 1 Day 1 (prior to infusion, at the time of completion of infusion [± 5 minutes], 2 and 6 hours post completion of infusion [± 15 minutes, Cohorts 1 through 5 and the expansion phase only]), Day 1 of all subsequent cycles prior to dosing, at the time of discontinuation of MEDI-573 and at 30 days after the last dose of MEDI-573. All ECGs should be done prior to the PK draw for corresponding timepoints. Electrocardiograms will be transmitted and interpreted by a central vendor selected by the Sponsor.

3.7.4 Disease Evaluations

Tumor measurements and assessments will be based on RECIST (Therasse et al, 2000) and will be performed as specified in [Table 3.6-1](#) and [Table 3.6-2](#) (Schedule of Subject Evaluations: Screening and Treatment Periods) and [Table 3.6-3](#) (Schedule of Subject Evaluations: Follow-up Periods). Additional tumor measurements may be performed at the discretion of the investigator or according to institutional practice. In subjects who achieve a complete or PR to treatment, tumor measurements will be repeated at least 4 weeks later using the same imaging tests. The same tumor assessment method should be used throughout the treatment period.

Tumor measurements must be recorded in metric notation by use of a ruler or calipers, and the same method/technique of tumor assessment must be used throughout the study. Whenever possible, tumor measurements will be conducted by the same person for a given subject. Imaging based evaluation is preferred to evaluation by clinical examination when both methods have been used to assess the antitumor effect of the treatment. The analysis for tumor response will be based on the investigator's assessment during the conduct of the study. Radiographic images may be collected and archived by the Sponsor or its designee.

Tumor assessments may include the following evaluations: physical examination, chest radiograph (x-ray), CT or MRI scan of the chest, abdomen, and pelvis, and CT scan or MRI of the brain. CT scan or MRI of the brain will be performed if the subject is neurologically symptomatic. The same method must be used for all subsequent tumor assessments. Bladder tissue and/or bladder cancer tissue obtained via cystoscopic biopsy, transurethral resection of bladder tumor (TURBT) or other surgical removal may also be acquired in the course of routine subject care, if the subject consents.

- Lesions detected by physical examination will only be considered measurable if superficial, eg, skin nodules and palpable lymph nodes. Documentation by color photography including ruler is recommended for estimating the size of skin lesions.

- Chest x-ray. Lesions considered acceptable for measurement on chest radiograph should be clearly defined and surrounded by aerated lung. However, CT is preferable.
- CT scans of the chest, abdomen, and pelvis. CT should be performed with contiguous cuts in slice thickness of 10 mm or less. Spiral CT should be performed using a 5-mm contiguous reconstruction algorithm.
- MRI scans. MRI is acceptable for measurement of lesions provided that the same anatomical plane is used for serial assessments. If possible, the same imaging device should be used for serial evaluations. In case of MRI, measurements will be preferably performed in the axial (transverse) plane on contrast enhanced T1 weighted images. However, there are no specific sequence recommendations.

Measurability of Tumor Lesions at Screening

At Screening, tumor lesions will be categorized as follows:

- **Measurable Lesions** - Measurable lesions are defined as those that can be accurately measured in at least one dimension (longest diameter to be recorded) as ≥ 20 mm with conventional techniques (CT, MRI, x-ray) or as ≥ 10 mm with spiral CT scan. All tumor measurements must be recorded in millimeters by use of a ruler or calipers.
- **Nonmeasurable Lesions** - Nonmeasurable lesions are defined as all other lesions (or sites of disease), including small lesions (longest diameter < 20 mm with conventional techniques or < 10 mm using spiral CT scan). Lesions considered truly nonmeasurable include the following: bone lesions, leptomeningeal disease, ascites, pleural/pericardial effusion, inflammatory breast disease, lymphangitis cutis/pulmonis, abdominal masses that are not confined and followed by imaging techniques, and cystic lesions.
- **Target Lesions** - All measurable lesions up to a maximum of 5 lesions per organ and 10 lesions in total, representative of all involved organs, should be identified as target lesions and recorded at Screening. Target lesions should be selected on the basis of their size (those with the longest diameter) and their suitability for accurate repeated measurements (either by imaging techniques or clinically). A sum of the longest diameter (LD) for all target lesions will be calculated and reported as the baseline sum LD. The baseline sum LD will be used as the reference by which to characterize the objective tumor response.
- **Non-Target Lesions** - All other lesions (or sites of disease) should be identified as non-target lesions and should also be recorded at Screening. Measurements of these lesions are not required, but the presence or absence of each should be noted throughout the study.

Response Criteria

Evaluation of Target Lesions

- **Complete Response (CR)** - Disappearance of all target lesions.
- **Partial Response (PR)** - At least a 30% decrease in the sum of the LD of target lesions, taking as reference the baseline sum LD.
- **Progressive Disease (PD)** - At least a 20% increase in the sum of the LD of target lesions, taking as reference the smallest sum LD recorded since the treatment started or the appearance of one or more new lesions.
- **Stable Disease (SD)** - Neither sufficient shrinkage to qualify for PR nor sufficient increase to qualify for PD, taking as reference the smallest sum LD since the treatment started.

Evaluation of Non-Target Lesions

- **Complete Response (CR)** - Disappearance of all non-target lesions and normalization of tumor marker level.
- **Incomplete Response/Stable Disease (SD)** - Persistence of one or more non-target lesion(s) or/and maintenance of tumor marker level above the normal limits.
- **Progressive Disease (PD)** - Appearance of one or more new lesions and/or unequivocal progression of existing non-target lesions. Unequivocal progression of an existing lesion can only be categorized as such if actual measurement with a ruler or caliper is not required and progression is obvious on visual inspection. For malignant ascites, PD is defined as an increase in abdominal girth (abdominal circumference measured at a fixed point at the level of the iliac crest) greater than 25% over baseline, with a worsening of clinical signs and symptoms. Malignant pleural or pericardial effusions will be considered PD only if there is worsening of associated symptoms.

Evaluation of Overall Response

Table 3.7.4-1 provides overall responses for all possible combinations of tumor responses in target and non-target lesions with or without the appearance of new lesions.

Table 3.7.4-1 Evaluation of Overall Response

Target Lesions (T)	Non-target Lesions (NT)	New Lesions	Overall Response
CR	CR	No	CR
CR	No-NT ^a	No	CR
No-T ^b	CR	No	CR
CR	Non-PD and not Unknown	No	PR
PR	Non-PD and not Unknown	No	PR

Table 3.7.4-1 Evaluation of Overall Response

Target Lesions (T)	Non-target Lesions (NT)	New Lesions	Overall Response
PR	No-NT	No	PR
SD	No-NT	No	SD
SD	Non-PD and not Unknown	No	SD
No-T	Non-PD and not Unknown	No	SD
PD	Any	Yes/No	PD
Any	PD	Yes/No	PD
Any	Any	Yes	PD
Unknown	Non-PD	No	Unknown
Non-PD	Unknown	No	Unknown

CR = complete response; PD = progressive disease; PR = partial response; SD = stable disease

^a No-NT is defined as no non-target lesions at baseline.

^b No-T is defined as no target lesions at baseline.

